8. Review of inclusion/exclusion criteria.

Subjects that continue to meet all eligibility requirements will be enrolled in the study and randomized 3:3:1 to one of three treatment arms. The subjects will then be administered their first dose of study drugs in the clinic.

TEAE monitoring will begin immediately following administration of the first dose of study drugs and will continue throughout the study. Any untoward medical occurrence that initiates or worsens after the first dose of study drugs and within 14 days of the last dose of study drugs will be recorded as a TEAE. Subjects will remain in the clinic under observation for one hour following their first dose and will be solicited for TEAE history prior to leaving the clinic. Prior to leaving the clinic, the following procedures will be performed:

1. Instruct subjects to continue to not take their prescribed BP medication;
2. Instruct subjects to continue to not take any NSAIDs, calcium channel blockers, or investigational drugs (other than the study drugs);
3. For WCBP: Instruct subjects to continue to use adequate contraceptive methods;

4. Provide subjects with sufficient study drugs for the remainder of the 2-week treatment period and instruct subjects to take the study drugs qd in the morning at home, except for the mornings of Days 6 and 13 when the drug will be taken in the clinic. The subjects will be instructed to take the Day 1-5 study drugs between 0700 and 1000 hours, and preferably at approximately the same time each day;
5. Provide subjects with a diary and instruct subjects to record any concomitant medications taken and details of study drug administration;
6. Instruct subjects to return to the clinic in 6 days (the morning of Day 6), and to bring the completed diary and study drug containers with any unused study drug.

6.3 Study Day 6

Subjects will return to clinic on the morning of Day 6 and will undergo the following procedures:

1. Solicit history of TEAEs since the previous visit;
2. Collect study drug containers and count and record unused study drug;
3. Review diary for details of study drug administration and any concomitant medications taken since the previous visit;
4. Provide subjects with ABPM, instruct in its use, and check the positioning of the ABPM.

Following the placement of the ABPM, the subjects will be administered their Day 6 dose of study drugs in the clinic. Prior to leaving the clinic, the following procedures will be performed:

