5. Subjects will be provided back their diary and instructed to record any concomitant medications taken and details of study drug administration;
6. Instruct subjects to return to the clinic in 6 days (on the morning of Day 13), and to bring the completed diary and study drug containers with any unused study drug.

If during the Day 7 visit, the subject's BP is too elevated for them to continue safely in the study (i.e., SBP_{24h} > 169 mmHg and/or DBP_{24h} > 110 mmHg), blood will be drawn for renal profile testing (see Section 8.5). The subject will be instructed to cease taking study drugs, instructed to resume taking their prescribed BP medication as directed by the study doctor or general practitioner, given back their diary and instructed to record any concomitant medications taken between visits, and instructed to return to the clinic in 7 days (Day 14).

6.5 Study Day 13

Subjects will return to clinic on the morning of Day 13 (except for those discontinued from study drug due to excessive hypertension or other safety reasons at Day 7) and will undergo the following procedures:

1. Solicit history of TEAEs since the previous visit;
2. Review diary for details of study drug administration and concomitant medications since the previous visit;
3. Collect study drug containers and count and record any unused study drug;
4. Provide subjects with an ABPM, instruct in its use, and check the positioning of the ABPM.

Following the placement of the ABPM, the subjects will be administered their Day 13 dose of study drugs (final dose) in the clinic. Prior to leaving the clinic, the following procedures will be performed:

1. Instruct subjects to wear the APBM at all times for the next 25 hours;
2. Subjects will be given back their diary and instructed to record any concomitant medications taken between visits;
3. Instruct subjects to return to clinic the following day (on the morning of Day 14), and to bring the completed diary to the clinic.

6.6 Study Day 14

Subjects will return to clinic on the morning of Day 14. The following evaluations will be performed:

1. Solicit history of TEAEs since the previous visit;
2. Review diary for details of concomitant medications since the previous visit;
3. Comprehensive physical examination (see Section 8.2);
4. Body weight while only wearing underwear and a light gown;
5. Vital signs (BP, pulse rate, respiration rate, and oral body temperature);

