APPENDIX D: ABPM PROCEDURE

D.1 ABPM Fitting Procedure

- D.1.1 The ABPM measurements will be collected with the Spacelabs 90207 monitor (Spacelabs Healthcare, Issaquah, WA, USA). The blood pressure monitoring equipment, both hardware and software, will be consistent across all subjects.
- D.1.2 The ABPM device shall be programmed to record measurements every 20 min between 09:00 and 21:59 and every 30 min between 22:00 and 08:59.
- D.1.3 The investigator shall ensure that a valid measurement is recorded manually upon fitting the monitor. This manual measurement shall take place between 07:00 and 10:00 on Day -1, Day 6, and Day 13. The date and time shall be noted in the subject diary.
- D.1.4 With the exception of Day 0, when study drug intake is in the clinic after determination of eligibility (and at least 25 hours after the Day-1 ABPM was initiated), Days 6 and 13, when study drug intake is at the time of fitting the ABPM device (following fitting) and Day 7, when study drug intake is 24 h \pm 1 h after the Day 6 dose, the subject shall be instructed to take the study drugs between 07:00 and 10:00, and preferably at approximately the same time each day.
- D.1.5 The subject shall be instructed to record bed time, rising time and drug-intake times in the subject diary.
- D.1.6 The ABPM shall be worn for a minimum of 25 h. This is the optimal duration, as it provides for a full 24 h after the white-coat window.

D.2 ABPM Removal Procedure

- D.2.1 The ABPM may be removed from the subject once 25 hours have elapsed since the recorded time of the first study measurement.
- D.2.2 The ABPM measurements shall be uploaded.

**APPENDIX E: WORLD MEDICAL ASSOCIATION DECLARATION OF HELSINKI
(OCTOBER 2013)**

WMA Declaration of Helsinki - Ethical Principles for Medical Research Involving Human Subjects

Adopted by the 18th WMA General Assembly, Helsinki, Finland, June 1964
and amended by the:

29th WMA General Assembly, Tokyo, Japan, October 1975

35th WMA General Assembly, Venice, Italy, October 1983

41st WMA General Assembly, Hong Kong, September 1989

48th WMA General Assembly, Somerset West, Republic of South Africa, October 1996

52nd WMA General Assembly, Edinburgh, Scotland, October 2000

53rd WMA General Assembly, Washington DC, USA, October 2002 (Note of
Clarification added)

55th WMA General Assembly, Tokyo, Japan, October 2004 (Note of Clarification added)

59th WMA General Assembly, Seoul, Republic of Korea, October 2008

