### Peak and trough

SBP and DBP at the expected peak and trough amlodipine concentrations will be summarized for the ITT population by treatment group at Day 6 and Day 13 by descriptive statistics (n, mean, SD, median, and range). Additionally, the difference between Day 6 and Day 13 will be calculated and summarized by descriptive statistics (n, mean, SD, median, and range).

For each variable (SBP peak, SBP trough, DBP peak, and DBP trough) a comparison between treatment groups will be performed with a two-sample t-test of the change from Day 6 to Day 13. A LOCF method of imputation will not be applied for missing values. The p-value will be evaluated on a two-sided t-test.

The trough BP (SBP and DBP) is the ambulatory BP measurement taken closest to the time of study drug administration on Study Day 6 or Day 13, respectively, that is also before the time of study drug administration that day. If there is no ambulatory measurement prior to administration of study drug on Study Day 6 or Day 13, the first ambulatory measurement after study drug administration that day will be used as trough.

The peak BP (SBP and DBP) is the ambulatory BP measurement taken closest to the time point 9 hours after study drug is administered on Study Day 6 or Day 13, respectively, that is also before the time point 9 hours after the study drug is administered that day. Based on the approved labeling for amlodipine besylate tablets, the expected peak time for amlodipine is 6 to 12 hours after the medication is administered, and thus the midway point (9 hours) was selected for this analysis.

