#### ABPM Study Measurements

A measurement shall be regarded as valid if it contains values for systolic blood pressure (SBP), diastolic blood pressure (DBP) and heart rate (HR) and

SBP is between 50 mmHg and 300 mmHg.

DBP is between 40 mmHg and 150 mmHg.

Pulse pressure is between 10 mmHg and 150 mmHg.

HR is between 40 bpm and 150 bpm.

The first study measurement shall be

The nearest valid measurement to the drug intake time on the day the monitor is fitted that is both a) between 07:00 and 10:00 and b) within 15 minutes of the drug intake time.

If there is no valid measurement within this period, a 1-hour grace period is permitted. It is, therefore, the nearest valid measurement to the drug intake time on the day the monitor is fitted that is both a) between 06:00 and 11:00 and b) within 75 minutes of the drug intake time.

If there is no valid measurement within this period, or if no drug intake time is recorded (e.g., Day-1), the first valid measurement recorded between 07:00 and 10:00.

If there is no valid measurement within this period, the first valid measurement recorded between 06:00 and 11:00.

If there is no valid measurement within this period, the nearest valid measurement to the drug intake time on the day the monitor is fitted, if that is recorded, or first valid measurement otherwise.

Measurements recorded during the first hour, from the first study measurement, shall be regarded as white-coat window measurements. The period covered by these measurements defines the white-coat window.

The last study measurements shall be

The earliest valid measurement that is a) at least 25 h after the first study measurement b) at least 25 h after the drug intake time on the day the monitor is fitted and c) less than 25 h after the end of the white-coat window

If there is no valid measurement within this period, a 1-hour grace period is permitted. It is, therefore, the earliest valid measurement that is a) at least 24 h after the first study measurement b) at least 24 h after the drug intake time on the day the monitor is fitted and c) less than 26 h after the end of the white-coat window

If there is no valid measurement within this period, the latest measurement that is less than 26 h after the end of the white-coat window.

Measurements before the first study measurement and measurements after the last study measurement shall be disregarded.

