Invalid measurements and measurements that result in an error shall not be regarded as study measurements.

Measurements recorded during the white-coat window are not included in daytime, night-time and 24 h statistics.

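### SAP 7.10 takes trough and peak BP from one reading each, and the trough reading is of a kind Appendix A keeps out of the ABPM averages; averaging readings already recorded would gain precision

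*SAP*

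**What the plan says.** SAP 7.10 (Peak and trough) defines trough in one sentence: "The trough BP (SBP and DBP) is the ambulatory BP measurement taken closest to the time of study drug administration on Study Day 6" (the same rule applies on Day 13), and it must precede the dose. A fallback follows: "If there is no ambulatory measurement prior to administration of study drug on Study Day 6 or Day 13, the first ambulatory measurement after" the dose serves as trough. Peak is the single reading closest to, and before, 9 h post-dose; 9 h is chosen as the midpoint of the labelled 6 to 12 h range. The change from Day 6 to Day 13 is compared between arms with a two-sided two-sample t-test, without LOCF.

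The visit sequence fixes where the trough reading comes from.

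- Protocol 6.3: "Following the placement of the ABPM, the subjects will be administered their Day 6 dose of study drugs in the clinic".
- Protocol 6.5: "Following the placement of the ABPM, the subjects will be administered their Day 13 dose of study drugs (final dose) in the clinic".
- Protocol Appendix D, D.1.3: "The investigator shall ensure that a valid measurement is recorded manually upon fitting the monitor", between 07:00 and 10:00.

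SAP Appendix A anchors the recording on the first study measurement, by preference this one: "The nearest valid measurement to the drug intake time on the day the monitor is fitted", within 15 minutes of intake. Earlier readings are disregarded, and the first hour from that measurement is the white-coat window. On that window it says: "Measurements recorded during the white-coat window are not included in daytime, night-time and 24 h statistics". Protocol D.1.6 adds: "The ABPM shall be worn for a minimum of 25 h", so that 24 h remain once the window is removed.

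**The concern.** The only readings that can precede the Day 6 or Day 13 clinic dose are the manual one at fitting and any scheduled one between fitting and dosing. The trough is therefore one reading, taken around fitting in clinic, at a time the plan treats as unsuitable for its averages. If no such reading exists, a post-dose value is labelled trough. The SAP does not say whether the manual fitting reading counts as ambulatory; if it does not, the fallback would be used more often and would mix pre-dose and post-dose values.

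Peak lies well outside the white-coat window but is also one reading. Both the trough and the peak comparison therefore carry full single-reading noise on both days, while the same recordings hold many more readings at relevant times.

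**Working it through.** **1. The plan's own figure.** 25 h of wear minus a 1 h white-coat window leaves 24 h, as D.1.6 states.

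**2. Where the trough reading falls.** Inputs from the documents: fitting at 07:00-10:00 with a manual reading; readings every 20 min from 09:00 to 21:59 and every 30 min otherwise (D.1.2); the Appendix A rules. Assumptions: dosing 1-30 min after fitting and no later than 10:00, clock-aligned scheduled readings, and the manual reading counted as ambulatory. Taking every minute gives 4,965 fitting and dosing combinations.

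- Trough reading inside the white-coat window: 2,925.
- Trough reading before the first study measurement: 2,040.
- Trough reading entering the day, night or 24 h averages: 0.

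These are counts of possible timings, not expected frequencies. The previous dose was taken at home between 07:00 and 10:00, so the fitting-time reading can fall from 21 h (10:00 to 07:00) to 27 h (07:00 to 10:00) after it.

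**3. What else the recording holds.**

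- Peak: 6-12 h after a 07:00-10:00 dose runs from 13:00-19:00 to 16:00-22:00, on the 20-minute schedule. That is 6 h / 20 min = about 18 readings.
- Trough after the Day 13 dose: no further dose follows. There are 5 to 8 scheduled readings from 22 h to the end of the 25 h recording, of which 4 to 5 lie at 22-24 h.
- Trough after the Day 6 dose: the Day 7 home dose is due at 24 h ± 1 h. There are 4 to 5 readings if it is taken at 24 h, and 2 if at 23 h.

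**4. Precision.** The documents give no single-reading SD, so it is assumed to be s = 9 to 13 mmHg, with day-to-day SD d. For the mean of k readings with within-window correlation r on both days:

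SD of change = √(2 × [s²(1 + (k − 1)r)/k + d²])

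One reading, d = 5:

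- s = 9: √(2 × (81 + 25)) = 14.6
- s = 13: √(2 × (169 + 25)) = 19.7

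Four independent readings, d = 5:

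- s = 9: √(2 × (20.25 + 25)) = 9.5
- s = 13: √(2 × (42.25 + 25)) = 11.6

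Confidence intervals shrink in the same ratio as the SD:

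| Case | SD of change, one reading | SD of change, window mean | CI narrower by |
|---|---|---|---|
| 4 readings both days, d = 5, r = 0 | 14.6-19.7 | 9.5-11.6 | 35-41% |
| 2 readings on Day 7, 4 on Day 14, d = 5, r = 0 | 14.6-19.7 | 10.5-13.3 | 28-33% |
| 4 readings both days, d = 10, r = 0 | 19.0-23.2 | 15.5-16.9 | 18-27% |
| 4 readings both days, d = 5, r = 0.5 | 14.6-19.7 | 12.3-16.2 | 16-18% |

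The second row uses √(s²/2 + s²/4 + 2d²). For scale, with 45 per arm (Protocol Appendix H) the 95% half-width is 1.96 × SD × √(2/45). That is 6.0-8.1 mmHg with one reading and 3.9-4.8 mmHg in the first row.

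**The case against.** Several points on the other side are sound.

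- **A reader might infer that the planned test is biased. The documents do not support that.** SAP 7.10 tests only the between-arm difference in Day 6 to Day 13 change. A clinic effect present on both days and in both arms largely cancels, and no peak-versus-trough contrast is planned. Its size is not given; only the descriptive trough levels are exposed.
- **A reader might infer that the value is not a trough.** Apart from the fallback, it is a pre-dose reading and so a genuine trough for the previous dose. The weakness is the setting and the single reading.
- **A reader might infer that 7.10 contradicts Appendix A.** The white-coat exclusion names only the daytime, night-time and 24 h statistics, and 7.10 sets its own selection rule. This is a choice of analysis, not a conflict.
- **A reader might take the 22-24 h readings as undisturbed home readings.** That is not assured. Subjects return to clinic on the morning of Day 14, and at participating sites a PK sample is due at 24 h ± 1 h, so readings from about 23 h may be in clinic. On Day 7 the home dose can end the window at 23 h.

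The alternative has its own costs. For a 07:00 dose, 22 h later is 05:00, inside the plan's night-time period (01:00-06:00), so the window can mix late-night and waking readings according to dose time. The Day 6 trough would follow the Day 6 dose, that is seven doses instead of six, while the label (Protocol Appendix F, 12.3) puts amlodipine steady state at 7 to 8 days. Under SAP 1.3.1 efficacy validity rests on the daytime count alone, so a recording may end before 22 h, and without LOCF that subject drops out. All of this stands and argues for adding the window means, not substituting them. It does not weaken the case for peak, where the roughly 18 readings avoid these problems.

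**Conclusion.** The point holds as a minor matter of precision. Trough and peak each rest on one reading. The trough reading is taken around fitting in clinic, or after the dose by fallback, and Appendix A excludes such readings from the ABPM averages as white-coat or as earlier than the first study measurement. The cost is mainly wider confidence intervals for the Day 6 to Day 13 comparison, plus descriptive trough levels that may carry a clinic effect of unknown size. The case is clearest for peak.

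The likely gain from averaging runs from 16-18% to 35-41% narrower intervals. It depends on assumed values: single-reading SD 9-13 mmHg, day-to-day SD 5 or 10, two to four readings per window, and correlation 0 or 0.5. The upper figures need four independent readings on both days and should not be quoted alone. These are additional efficacy variables, outside the primary endpoint and the secondary hierarchy, and neither is affected.

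**What to change.** Add to SAP 7.10 a supplementary analysis, labelled post-unblinding because SAP v4.0 is itself listed as a post-unblinding version:

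- **Peak:** mean of valid readings 6-12 h after the Day 6 and Day 13 doses.
- **Trough:** mean of valid readings 22-24 h after those doses, with the Day 6 window cut off at the diary-recorded Day 7 dose time.
- **Minimum count:** a stated number of valid readings per window (two is attainable even when the Day 7 dose is taken at 23 h), with the number of subjects failing it reported by arm.

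Keep the single-reading definitions alongside. State whether the manual fitting reading counts as ambulatory, and report how often the post-dose fallback was used.

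The cost is SAP wording, programming for one additional analysis and a further disclosed post-unblinding addition. No new data are needed. Some subjects will be missing from the trough window mean.

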### **Sensitivity analyses**

A sensitivity analysis will be conducted to insure the change in definition of the ITT population (see Section 1.3.2) does not impact the study conclusions. A mITT population will be based on the definition originally presented as the ITT population in the protocol (valid Baseline and at least one valid follow-up ABPM measurement) and a second set of analyses will be conducted purely to demonstrate the definition does not have an impact on the primary and secondary efficacy analyses. The following analyses will be conducted:

1. mITT for SBPday
2. mITT for SBP24h
3. mITT for DBP24h

The impact of defining valid ABPM measurements based on valid daytime measurements for the efficacy analyses (see Section 1.3.1 for further detail) is that the analyses of the secondary ABPM efficacy parameters (SBP24h and DBP24h) and exploratory ABPM efficacy parameters (SBPnight and DBPnight) may include invalid measurements with respect to the 24-hour period (i.e., may not meet criterion d or e in Section 1.3.1) or night-time period (i.e., may not meet criterion d in Section 1.3.1), respectively. It is anticipated that this will be a very small number of cases and will not impact the secondary and exploratory ABPM efficacy conclusions drawn. Sensitivity analyses will be conducted to verify this point. The following analyses will be conducted:

1. ITT for SBP24h excluding SBP24h values that had an entry of valid for day validity and an entry of invalid for night or 24h validity (i.e., did not meet criterion d or e, respectively)
2. ITT for DBP24h excluding DBP24h values that had an entry of valid for day validity and an entry of invalid for night or 24h validity (i.e., did not meet criterion d or e, respectively)
3. ITT for SBPnight excluding SBPnight values that had an entry of valid for day validity and an entry of invalid for night validity (i.e., did not meet criterion d)
4. ITT for DBPnight excluding DBPnight values that had an entry of valid for day validity and an entry of invalid for night validity (i.e., did not meet criterion d)

To assess the impact of baseline, a further sensitivity analysis will be conducted on the primary endpoint (mean change of SBPday) using a regression model adjusted from Baseline on ITT, mITT, and PP populations.

### **Exploratory efficacy analyses**

Exploratory efficacy analyses will include two-sample t-tests to test one-side hypotheses of superiority for pairwise comparisons between treatment arms 1 and 2, 1 and 3, and 2 and 3 for DBPday, SBPnight and DBPnight.

Further, two-sample t-tests to test one-side hypotheses of superiority for pairwise comparisons between treatment arms 1 and 3 and 2 and 3 will be performed for SBPday, SBP24h, and DBP24h (the comparison of treatment arms 1 and 2 for these endpoints are covered separately under the respective primary and secondary efficacy analyses).

All exploratory efficacy comparisons will be based on the mean reduction in BP from the baseline (Day -1 to Day 0) ABPM measurement to the Day 13 to Day 14 ABPM measurement (or if a LOCF was required, the Day 6 to Day 7 ABPM measurement). The analyses will use the ITT data set including LOCF (and MMRM if possible) for subjects who were withdrawn from treatment early. Sensitivity analyses will be used to compare these results to those of the PP data set.

